8.0 Procedures Involved

8.1 *Describe and explain the study design:*

This is a within-subject analysis plan where participants receive at least 3 beverages and undergo blood draw, indirect calorimetry measurements, and an MRI scan.

8.2 *Provide a description of:*

- *All research procedures being performed*
- *If the study has more than one procedure, session, and/or subject population, describe each procedure, session, and/or study population separately. For complex studies, you are encouraged to include a figure or chart.*

PILOT STUDY:

Overview

The sugars and non-nutritive sweeteners will be using in our full study all have different levels of sweetness due to their chemical structures. To decide what amounts of each of these to use, we will conduct a) pilot study, in which a convenience sample of participants (~20) will taste and rate a variety of mixtures of sugars and non-nutritive sweeteners. To reduce the potential for "tasting fatigue," only a limited number of mixtures will be tasted during a single 2-hour session, but participants will be allowed to complete as many pilot study sessions as they choose.

Recruitment

A convenience sample of participants will be recruited primarily via word-of-mouth or email from our lab's Ripple database (see section 9.4 for information about Ripple). Emails will be generated for individuals who opted-in to contact about participation in future studies with our lab when they filled out a screening survey. See supporting documents for email wording.

[figure not shown]
Informed Consent

Participants will be sent via email the consent form for the study at least 24 hours in advance of their scheduled consent session. Upon arrival for the session, participants will have ample time to review and sign the consent form prior to beginning the training session. Research personnel will be available to answer any questions the participant may have.

Flavor and Sweetness Ratings

Participants will be trained on how to use standard perceptual rating scales used in the study. Then, they will taste, rate, and rank each mixture using these scales. All mixtures will be within common sweetness concentrations found in commercially available beverages (i.e., we will not provide sugar or non-nutritive sweetener amounts that would commonly cause gastrointestinal discomfort in most people). Data from this pilot study will then be used to determine acceptable concentrations of sugars and non-nutritive sweeteners to be used in the full study.

FULL STUDY:

OVERVIEW:

Approximately 200 participants will be recruited from the general public for this randomized crossover study conducted at the FBRI. Our goal is to have approximately 140 participants complete the study. The duration of participation will be no more than 6 weeks for each aim. The figure above depicts the overall study design and procedures for both Aims 1 and 2. The study design is the exact same for Aims 1 and 2, but the beverages selected for conditions "CS1, CS2, and CS3" are different, depending on aim. For Aim 1, conditions will include fructose, glucose, and sucrose. For Aim 2, conditions will include sucrose, high fructose corn syrup (HFCS), and non-nutritive sweetener+sucrose. Each CS drink will be consumed over a 1-week period in sequential weeks without "washout" weeks in between.

Recruitment and Screening:

Approved study recruitment materials will be distributed in the following ways. Flyers will be posted on bulletin boards and approved posting sites throughout Roanoke, Blacksburg, and surrounding areas. Digital advertisements will be displayed on [name] lab and CHBR social media, VT News, and in list serves with permission. All advertisements will include a link to the lab website where there will be approved language describing the research study. Interested participants will fill out a general screening survey. All screening surveys will be delivered through Ripple (a HIPAA-compliant, secure database software; see section 9.4 for description). This screening survey will be used to determine study eligibility. Once the general screening survey has been completed, participants who may be eligible for this study will be contacted via email (see attachment 'Screening email'). If participants choose to complete the study-specific screening form and are eligible for this study, they will be contacted to schedule a consent session.

CONSENT SESSION (Called "pretest" in study design figure above) (~2.5 hours):

Informed Consent

Participants will be sent via email the consent form for the study at least 24 hours in advance of their scheduled consent session. Upon arrival for the session, participants will have ample time to review and sign the consent form prior to beginning the training session. Research personnel will be available to answer any questions the participant may have.

Anthropometrics and Clinical Measures

Participants' height, weight, hip circumference, and waist circumferences will be measured. Height will be measured using a stadiometer, weight using a body weight scale, and waist and hip circumference using a standard Gulick tape measure. A fingerstick blood sample will be collected for point-of-care hemoglobin A1C assessment to ensure eligibility. A lancing device and single-use lancet will be used to obtain a finger stick. A point-of-care A1C analyzer and appropriate cartridges will be used to assess hemoglobin A1C.

Flavor Ratings

The participants will first be trained by the researcher on how to use the standard perceptual rating scales. Then participants will taste and make ratings of beverages using the standard rating scales. After the participant has completed the tasting protocol, the researcher will determine three flavors to be used in the beverages the participants will consume during the behavioral conditioning sessions.

Mock MRI Training

Participants will also complete a "mock" MRI training, in which they learn to swallow small amounts of liquids while lying supine. (Note: most people have no difficulty learning to swallow small quantities of liquid while lying down). This training will be performed in an MRI simulator that is the same bore size and similar environment to the real scanner, but does not contain a magnetic field. Participants who have difficulty with supine swallowing or who express discomfort in the simulated fMRI environment may be excluded from the study or only undergo portions of the study that do not involve fMRI scanning. If not completed during the consent session, participants will be asked to complete this training as part of another conditioning session. Compensation for this "mock" scan is built into the compensation for the consent session.

Dietary Intake

Participants will be instructed to consume the same breakfast meal the morning of each conditioning session and lunch beverage exposure (described below, see In-Person Conditioning Sessions and At-Home Conditioning Sessions). The breakfast meal will be approximately 20% of their estimated total daily energy needs and composed of ~15% of calories from protein, 30% from fat, and 55% from carbohydrate. Estimated energy needs will be calculated using a validated equation that uses the participant's height, weight, sex, and age. Participants will work with research personnel to develop the appropriate meal choice to meet the specified nutrient composition and fit their individual preferences. Participants will be responsible for preparing these meals at home. They will be instructed to consume only plain water after finishing this meal until their scheduled conditioning session.

Dietary, Physical Activity, and Health Behavior Questionnaires

After the training session, participants will receive an email containing links to dietary-physical activity- and behavior-related questionnaires in REDCap to complete. It is estimated that it will take the participant approximately 45 minutes to complete all of the

questionnaires. These questionnaires will be sent using the automated invitation function in REDCap, which will generate an email containing unique links for each survey for each participant. Only participant email addresses will be stored as participant identifiers to track survey responses for data collection.

IN-PERSON CONDITIONING SESSIONS (~4 hours each, ~12 hours total):

These sessions will occur in sequential weeks with at least 3 days in between in-person sessions.

Fast and Refrain from Exercise

Participants will be asked to refrain from exercise for at least 24 hours and fast for at least 3 hours prior to each conditioning session.

Consumption of Planned Breakfast Meal

Participants will be instructed to consume the same breakfast meal the morning of each conditioning session. They will have planned this meal with research personnel during the consent session. They will be responsible for procuring and/or preparing these meals at home. They will be instructed to consume only plain water after finishing this meal until their scheduled conditioning session or take-home lunch beverage consumption time.

Internal State Ratings

Participants will rate their hunger, thirst, and fullness on standard visual analog scales while fasted and after consumption of the beverage, along with perceptual ratings about the beverages consumed during the session.

IV Blood Draws

An IV catheter will be inserted into the participant's arm for venous blood draws throughout the session. This catheter will remain in the participant's arm for the duration of the session (~4 hours). A fasting baseline draw will be made, and then six additional blood draws after the participant consumes the conditioning beverage will be conducted throughout the remaining session. Two tubes of no more than 5 ml each will be collected at each blood draw (14 tubes total). This is approximately 126 ml of blood in total (~8-9 tablespoons). This is roughly equivalent to 1/4 the amount of blood given during a typical blood donation. All blood draws will occur while the participant is reclining on a bed inside a metabolic chamber (see Metabolic Chamber Indirect Calorimetry below). For the draws, the researcher performing the blood draws will reach their arms into the chamber via ports on the side of the chamber walls. Participants will be able to communicate with research personnel using a 2-way intercom system, and the walls of the metabolic chamber are clear plexiglass that allow researchers and participants to see each other throughout the measurement. IV blood draws occur concurrently with metabolic chamber measurements (see below). The IV catheter line will be flushed with normal saline between each blood draw to prevent coagulation in the catheter tubing. After the final blood draw, the catheter will be removed and the venipuncture site secured with sterile tape or bandage. Should the IV catheter placement fail or become unusable during the session, the catheter will be removed and participants will continue with the metabolic chamber indirect calorimetry portion of the session.

Metabolic Chamber Indirect Calorimetry

Participants will rest reclined on a bed inside the metabolic chamber for the duration of the measurement. The chamber is an open-circuit system in which fresh air is pumped into the room at a specified flow rate. Metabolic chamber measurements involve non-invasive collection and measurement of oxygen and carbon dioxide concentrations expired through respiration. Metabolic chamber measurements occur concurrently with IV blood draws (see above). Participants will be able to communicate with research personnel using a 2-way intercom system, and the walls of the metabolic chamber are clear plexiglass that allow researchers and participants to see each other throughout the measurement. A fasting measurement will be collected for approximately 30-60 minutes; during this time a fasting blood draw will also be collected (see IV Blood Draws above). After the fasting measurement, participants will consume the conditioning beverage, and a post-beverage measurement will be collected for approximately 3 hours.

Beverage Consumption

Participants will consume the single 355 ml, 110 kcal conditioning beverage within 5 minutes. The conditioning beverage contains flavoring, citric acid (commonly used in sugar-sweetened beverages [e.g., Gatorade]), deionized water, and the sugar or sugar + non-nutritive sweetener stimuli being tested. Participants will rate their hunger, thirst, and fullness on standard visual analog scales after consumption of the beverage, along with perceptual ratings about the beverages consumed during the session.

Take-Home Beverages

At the end of the session, participants will be provided 5 bottles of the same conditioning beverage to be consumed at home. One bottle will be used for the at-home conditioning session (see below), and the remaining 4 total bottles will be consumed at the following times: 1 hour before dinner the same day as the in-person and at-home conditioning sessions (1 bottle for each conditioning session), and 1 hour before lunch the day following the in-person and at-home conditioning session (1 bottle for each session).

AT-HOME CONDITIONING SESSIONS (~15 minutes each, 45 minutes total):

Fast and Refrain from Exercise

Participants will be asked to refrain from exercise for at least 24 hours and fast for at least 3 hours prior to each conditioning session.

Consumption of Planned Breakfast Meal

Participants will be instructed to consume the same breakfast meal the morning of each at-home conditioning session. They will have planned this meal with research personnel during the consent session. They will be responsible for procuring and/or preparing these meals at home. They will be instructed to consume only plain water after finishing this meal until their scheduled conditioning session time.

Zoom Monitoring of Consumption

A Zoom link will be sent to the participant prior to the scheduled at-home conditioning session time. During the session, participants will turn their camera on to allow the

researcher to watch them drink the conditioning beverage. This session will NOT be recorded. At the end of the session, participants will be reminded to consume the take-home beverages at the appropriate specified times: 1 hour before dinner the same day, and 1 hour before lunch the following day. Participants will be sent an automated email with a link to a REDCap survey. Participants will rate their hunger, thirst, and fullness on standard visual analog scales before and after consumption of the beverage, along with perceptual ratings about the beverages consumed during the session on this survey.

TAKE-HOME BEVERAGE CONSUMPTION (~5 minutes each, 60 minutes total):

Consumption of Planned Breakfast Meal

Participants will be instructed to consume the same breakfast meal the morning of each lunch beverage consumption time. They will have planned this meal with research personnel during the consent session. They will be responsible for procuring and/or preparing these meals at home. They will be instructed to consume only plain water after finishing this meal until their scheduled lunch beverage consumption time.

Consumption of Take-Home Beverages

Participants will be instructed to consume the take-home beverages 1 hour before dinner the same day as their conditioning session (either in-person or at-home; see above) and 1 hour before lunch the day following their conditioning session (either in-person or at-home). Participants will be sent surveys to verify beverage consumption times and amounts via REDCap. These surveys will be sent using the automated invitation function in REDCap, which will generate an email containing unique links for each survey for each participant. Only participant email addresses will be stored as participant identifiers to track survey responses for data collection.

POST-TEST SESSION (~3 hours):

Fast and Refrain from Exercise

Participants will be asked to refrain from exercise for at least 24 hours and fast for 3 hours prior to each conditioning session.

Internal State Ratings

Participants will rate their hunger, thirst, and fullness on standard visual analog scales while fasted and periodically throughout the session.

Flavor Ratings

Participants will taste and make ratings of flavored beverages using standard rating scales. These are the same beverages and flavors used throughout the study.

MRI Scan

The MRI scan will occur at the Human Neuroimaging Laboratory at FBRI. MRI safety will be reviewed with the participant by an FBRI-approved scanner operator prior to entering the scanner room containing the magnet. Participants and experimenters will remove metal from their bodies and clothing (e.g., jewelry, cell phones, coins, etc.). Participants will also complete an MRI safety form to ensure they qualify to have an MRI performed (included in supporting documents). Prior to entering the scanner room with

the magnet, experimenters will use a metal detection wand to scan over the participant to ensure no metal that could be subject to the magnet's pull is detected (e.g., zippers or grommets on clothing cannot be pulled off by the magnet). Inside the scanner room, participants will lie on a table that slides into the bore of the scanner. Using a head coil, functional images will be acquired using an EPI bold sequence. Participants will wear disposable earplugs and other ear protection to minimize the amount of noise heard during the scan (magnetic field gradient changes during the scan can be loud).

Participants are able to communicate with the experimenter via either a speaker and microphone system (between scanning segments) or with an emergency squeeze ball (during scan acquisition). Participants will be instructed to talk with experimenters between scanning segments via microphone-and-speaker system and to use the squeeze ball during scan acquisition for emergencies (e.g., they begin to feel claustrophobic during the scan). The experimenters will check in with participants periodically between scanning segments to ensure participant comfort.

Scanner Taste Tasks

Participants will taste small amounts of liquid stimuli that will be presented according to a standard paradigm we have successfully used before in taste MRI. In brief, hydraulic pumps will be used to pump solutions through plastic beverage tubing attached to a mouthpiece to the subject lying in the scanner. The mouthpiece will be sterilized and new beverage tubing will be used for each participant. The mouthpiece will be anchored to the head coil so that the end comfortably rests on the anterior tongue, just inside the participant's mouth. This will not interfere with breathing through the mouth, and participants will always be able to breathe through their noses. The solutions will be dispensed through one tube at a time. The overall flow rate of solution into the mouth will be very slow (~0.5ml of a liquid over ~3-5 seconds).

Ad Libitum Intake

Participants will be given access to bottles containing the conditioning beverages used during their study sessions for 30 minutes. They will be allowed to drink as much or as little of the beverages as they would like. Amounts of beverages consumed will be recorded as data.

Forced Choice

Participants will be offered the conditioning beverages used during their study and asked to choose one to take home with them. This is a measure of "forced choice" and will be recorded as data.

8.3 *Describe:*

- *Procedures or safeguards intended to reduce the probability and magnitude of risks. (For example: Reducing the risk of injury in a virtual reality study either by having the subjects sit during the study or by providing an obstacle-free space for walking.)*
- *Be sure to describe all drugs and devices used in the research, when they will be administered or used, and their purpose.*

- *Methods used to collect data about subjects. Please upload all data collection forms to Protocol Management. Some common examples are:*
 - *Screening questionnaires*
 - *Survey(s), including online surveys*
 - *Demographic questionnaire(s)*
 - *Interview guide(s), e.g., questions or pool of questions for semi-structured interviews*
 - *Focus group guide(s)*
 - *Other documents used to collect data*

Procedures or safeguards intended to reduce the probability and magnitude of risks: MRI. Every effort will be made to ensure the subject's comfort and to reduce any minimal risk. First and foremost, subjects will be thoroughly screened to make sure that MRI contraindications are not present. If, at any time, subjects experience discomfort, dizziness, or claustrophobia during the scan, they will have access to an emergency squeeze bulb which they can squeeze to get the attention of the experimenters. Experimenters will then check in with the subject, and if requested, subjects will be immediately removed from the MRI machine. Additionally, the staff operating the MRI will have completed Advanced MRI/Operator Training which is required for those persons wishing to conduct research on the Human Neuroimaging Lab (HNL) MRIs. Training consists of a safety training, full-day advanced user training, scanning observation, and hands-on practice, supervised scanning. Topics include safety and emergency procedures, subject preparation and screening, scanner set-up and operation, and troubleshooting. Each person must also complete at least 4 hours of observation (to include 2 different studies) and at least 16 hours of supervised scanning (to include 4 different studies). Certification is granted upon completion of the training and passing of a competency exam.

An MRI Safety Screening Form will be completed by each participant and reviewed by trained staff in order to ensure there are no contraindications to MRI scanning.

Venous Blood Draw. The potential risks associated with the blood draw procedure include hematoma from failure to use proper blood drawing techniques and infection if proper infection and control practices are not observed and used (WHO). These may be associated with some discomfort, but present very little danger to subjects' welfare. To reduce this risk, all blood draws will be performed by a trained and skilled medical technologist, phlebotomist, or nurse in the appropriate laboratory setting. In addition, a maximum of three attempts will be made to obtain blood during each individual blood draw. Rarely, a blood clot will form or infection, inflammation, or bleeding can occur at the site. If inflammation at the site does occur, we will apply a warm compress to the site and elevate the arm to reduce it.

Fingerstick Blood Draw. The potential risks associated with performing a fingerstick blood draw are minimal. The likely risks involve pain and bleeding in the fingertip at the collection site. Rarely, an infection may occur at the puncture site. To minimize these risks, participants and study staff will be trained on the proper technique for performing a capillary blood sample and how to care for the site after the sample is obtained.

Catheter Blood Draw: Some pain or discomfort may be experienced when the catheter is inserted in the vein, but this should persist for only a short time. During the blood draws, there may be pain and/or bruising at the site where the IV catheter is inserted. In about 1 in 10 or 10% of the cases, a small amount of bleeding under the skin will cause bruising. The risk of a blood clot forming in the vein is about 1 in 200, while the risk of infection or significant blood loss is 1 in 1000. There is a small risk of the vein becoming inflamed and/or painful in the hours or days after the needle is removed. To reduce this risk, all catheter placements and blood draws will be performed by a trained and skilled medical technologist, phlebotomist, or nurse. In addition, a maximum of three attempts will be made to insert the IV catheter at different sites. If the participant feels faint during or after a blood draw, research personnel will immediately have the participant lie back on the bed inside the metabolic chamber.

Metabolic Chamber Indirect Calorimetry: There are no known risks associated with the method of indirect calorimetry. However, some people may feel uncomfortable or anxious while inside the metabolic chamber. Participants will be able to breathe normally during the entirety of the testing procedure. They will also be able to see and communicate with the experimenter and will be able to tell the experimenter if they would like to terminate the measurement.

*8.4 What data will you collect during the study and how you will obtain them?
Please include descriptions of electronic data collection, database
matching, and app-based data collection:*

Ripple (see section 9.4 for Ripple description) will be used to collect screening information. Information about the beverages participants will be consuming at home as well as dietary, physical activity, and behavior information will be collected through REDCap. MRI safety information will be collected via paper form (included in supporting documents). Perceptual ratings will be collected using a laptop or tablet and custom scripts written in R or Python (PsychoPy). Blood glucose will be measured using a Hemocue point-of-care system, and insulin will be measured using the Immunolite 1000 Immunoassay System or ELISA. Other blood metabolites will be measured from stored samples using ELISAs or other appropriate wet lab equipment and techniques. Brain images will be acquired during fMRI scans. Metabolic measurements will be collected using a metabolic chamber from MEI Research, Ltd. All data collected during the study will be stored on FBRI's instance of REDcap and/or FBRI's secured server.

8.5 Who will transcribe or code audio and/or video recordings?:

There will be no audio or video recordings.

8.6 Include a description of any deception to be used in the study. Include justification for the use of deception (why the deception is necessary), describe the debriefing process, and describe how the study meets all the following criteria for alteration of consent (deception is considered an alteration of informed consent):

- *The research involves no more than minimal risk to the subjects*
- *The alteration will not adversely affect the rights and welfare of the subjects*
- *The research could not practicably be carried out without the alteration/deception*
- *(Optional but encouraged in most cases) Subjects will be provided with additional pertinent information after participation (i.e., debriefing for studies involving deception)*

There will be no deception.

8.7 If the study involves long-term follow-up (once all research related procedures are complete), describe what data will be collected during the follow up period and when it will occur:

There are no long-term follow-ups.

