9.0 Data and Specimen Long Term Storage and Use

9.1 If you will store data or specimens for future use, describe where you will store the data or specimens, how long they will be stored, and how and by whom the data or specimens will be accessed:

Indirect calorimetry data will be stored on a secure network drive provided by FBRI. Behavioral (e.g., last time food eaten before measurement, last bout of exercise before measurement, etc.), anthropometric, responses to questionnaires, and pertinent metabolic variables will be stored in FBRI's

instance of REDCap. Data will be stored indefinitely for future analysis and use in developing future protocols. Only individuals with FBRI access to secure network drives and FBRI's instance of REDCap will have access to stored data. Plasma and/or serum aliquot samples will be frozen and stored for future analysis of insulin and other metabolites. Additional aliquots of plasma and/or serum will be stored indefinitely after the completion of data analysis to allow for replicate testing to ensure data quality and for additional analyses as the field moves forward.

9.2 For specimens, list the data to be stored or associated with each specimen:

Serum and plasma blood samples for storage will be labeled with the participant's 4-digit ID number, date collected, and conditioning beverage associated with that sample.

9.3 Describe the procedures to release data or specimens outside of the research team, including the process to request a release, approvals required for release, who can obtain data or specimens, and what data will be provided with specimens:

No specimens will be released.

9.4 Describe the identifiers to be included with stored data or specimens, as well as any key or code that could be used to make them identifiable. Describe where the code will be stored, who will have access to it, and when it will be destroyed:

Data will be coded using a 4-digit sequentially-generated ID number unique to each participant. The key linking the participant name or identifiable information and the ID number will be stored in Ripple.

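### Breakfast content is standardised but its timing is not: the minimum-only fast lets the breakfast-to-drink interval differ between a participant's three sessions, and the recorded time of last food is not used in the analysis

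*Combined protocol and SAP*

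**What the plan says.** Section 8.2 (Dietary Intake) fixes what is eaten. The breakfast is "approximately 20% of their estimated total daily energy needs and composed of ~15% of calories from protein, 30% from fat, and 55% from carbohydrate", planned individually with staff. On repetition, the in-person session text says: "Participants will be instructed to consume the same breakfast meal the morning of each conditioning session". After it, only water is allowed: "They will be instructed to consume only plain water after finishing this meal until their scheduled conditioning session".

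On timing, the in-person session text asks participants to "fast for at least 3 hours prior to each conditioning session". No maximum, target interval or clock time is given, and nothing requires a participant's three sessions to match.

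Within the session, the chamber text says: "A fasting measurement will be collected for approximately 30-60 minutes", with a fasting blood draw in that period. Then: "After the fasting measurement, participants will consume the conditioning beverage, and a post-beverage measurement will be collected for approximately 3 hours". The drink is 355 ml and 110 kcal.

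Section 4.1 lists indirect calorimetry and blood glucose among the primary endpoints. Section 5.2 analyses changes in calorimetry measures, glucose and insulin with linear mixed effects models and names no covariates. Section 9.1 gives, as examples of stored behavioural data, "last time food eaten before measurement, last bout of exercise before measurement".

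**The concern.** The beverage comparison is within person across three sessions, so anything that varies between one participant's sessions enters its error term. The plan controls the content of breakfast, which shows that breakfast is regarded as relevant to the outcomes, but leaves its timing loose. A participant could arrive 3 h after breakfast one week and 5 h after it another week and comply fully both times.

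If breakfast is still affecting glucose, insulin or substrate oxidation when the session starts, the two sessions begin at different points on a falling curve. Subtracting the pre-drink value removes a constant difference in level. It does not remove a decline that continues at a different rate through the 3-hour post-drink window. That remainder has nothing to do with the type of sugar. The plan lists the variable that could account for it among its stored data but does not put it in the model.

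**Working it through.** **1. The plan's own figure.** The target of 70 completers per aim cannot be reproduced, because section 14.1 gives no alpha, power, effect size or SD. Only the enrolment step can be checked: 140 / (1 - 0.30) = 200, which agrees with the plan.

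**2. Shortest breakfast-to-drink interval.** The 3 h runs to the session (8.2), and the drink follows a 30-60 minute baseline.
- 3 h + 0.5 h = 3.5 h; 3 h + 1 h = 4 h.
- No maximum is stated. The range allowed for the baseline adds up to 30 minutes of variation by itself.

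**3. Breakfast carbohydrate against the drink.** With daily energy needs E (assumed; not in the documents) and 4 kcal/g:
- Breakfast = 0.20 x 0.55 x E / 4 g. Drink = 110 / 4 = 27.5 g, if all its energy is sugar.
- The ratio is 0.11 x E / 110 = E / 1000.
- E = 1600: 44 g, ratio 1.6. E = 2000: 55 g, ratio 2.0. E = 2500: 69 g, ratio 2.5. E = 3000: 82.5 g, ratio 3.0.

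These are totals eaten, not what remains when the drink is taken.

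**4. Level difference, before baseline subtraction (illustration).** Assume carbohydrate oxidation = 4.55 x VCO2 - 3.21 x VO2 (g/min, gas volumes in L/min), VO2 = 0.25 L/min, and a respiratory ratio lower by d in the session starting 5 h after breakfast than in the one starting 3 h after. The difference over 180 minutes is 4.55 x 0.25 x d x 180:
- d = 0.01: 2.0 g; d = 0.03: 6.1 g; d = 0.04: 8.2 g.

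**5. What remains in the change score.** Assume the breakfast effect decays exponentially at rate k = ln 2 / half-life, and take d as the gap averaged over the baseline of length b hours. Relative to the gap at session start:
- baseline mean = (1 - exp(-kb)) / (kb)
- post-drink mean = (exp(-kb) - exp(-k(b + 3))) / (3k)
- fraction remaining = 1 - (post-drink mean / baseline mean)

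The extremes are:
- half-life 4 h, b = 0.5: 1 - 0.7151 / 0.9579 = 25%
- half-life 1 h, b = 1: 1 - 0.2104 / 0.7213 = 71%

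Applied to step 4:
- d = 0.03: about 1.6 to 4.4 g.
- d = 0.01 to 0.04: about 0.5 to 5.8 g, or 2-21% of 27.5 g.

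**6. What lost precision would mean (illustration).** Suppose 70 completers gave 80% power for a paired contrast (two-sided 0.05, normal approximation). If the variance of the within-person difference rose by 5%, 10% or 25%, power would fall to 78%, 76% or 71%, and 74, 77 or 88 completers would be needed to restore it. From 90%, power would fall to 89%, 87% or 83%. The documents do not show which increase applies, if any.

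**The case against.** The strongest case against is that the plan already controls much of this. Breakfast is identical each time and followed only by water, each session has its own fasting baseline, outcomes are changes, time of last food is stored, and not fasting is a possible ground for withdrawal (16.1). A take-home bottle is also due before dinner on the same day, which puts a practical limit on start times. All of this stands, and it narrows the problem. It does not make the interval the same across sessions.

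Three stronger readings are tempting, and the documents do not support them.
- **The drink may come 3 h after breakfast.** The 3 h ends at the session. The drink comes at 3.5-4 h at the earliest.
- **The disturbance is about 6 g, or 22% of the drink's carbohydrate.** That is the level difference in step 4 (6.1 / 27.5). Its constant part cancels in the change score, so only the remainder in step 5 counts. A single 3 h versus 5 h contrast is also not a variance. The noise depends on how widely intervals vary within participants, which the documents do not give.
- **The beverage estimates are shifted.** Section 8.2 describes a randomised crossover, with 70 completers planned per aim. Even with the unsubtracted slope of 6.1 / 2 = 3.07 g per hour and an assumed independent session-to-session SD of 1 h, the typical chance shift in a contrast is 3.07 x 1.41 / sqrt(70) = 0.5 g, about 2% of 27.5 g. That is ordinary sampling error, already reflected in the standard error.

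It is also fair to say that section 5.2 is brief and names no covariates at all, so this omission is not a singular oversight. No particular tolerance has a source in the documents, and fixing the start time alone would leave the baseline length free to vary.

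**Conclusion.** The point holds as an avoidable loss of precision that is cheap to remove. The text sets a minimum fast only, does not match interval or clock time across a participant's three sessions, and does not use the recorded time of last food. The outcomes affected are the primary calorimetry and blood glucose endpoints and the analysed insulin outcome, which section 4.1 does not list as primary.

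The size of the noise cannot be derived from the documents. The 0.5-5.8 g figure rests on the assumed decay shape, a half-life of 1-4 h, a respiratory-ratio gap of 0.01-0.04 and the assumed oxygen uptake. It shows that the residual need not be trivial beside a 27.5 g drink, not that it has that size. That breakfast is still having an effect when the drink is taken is plausible but is not stated in the plan. Provided the interval is unrelated to beverage condition, as randomised order should ensure on average, there is no systematic bias.

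**What to change.** Leave the stated fasting minimum as it is; its length is for the investigators.

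- **Section 8.2:** require each participant's three in-person sessions to keep the start time and breakfast-to-drink interval of that participant's first session, within a tolerance the investigators set (for example +/-30 minutes). Use one fixed baseline length, so that the interval to the drink is controlled as well as the interval to arrival. Record breakfast time at arrival and flag sessions outside the tolerance.
- **Section 5.2:** prespecify time since last food, which is already recorded, as a session-level covariate in the glucose, insulin and calorimetry models. It is determined before the drink is taken, so adjusting for it does not adjust away a beverage effect.

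The cost is slightly less flexible booking and one extra covariate. No visits, samples or staff are added.
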